## 7.2. Secondary Efficacy Endpoints and Analyses

For daytime/nighttime endpoints, only ABPM results denoted as "Valid" or "Valid within Acceptable Limits" may be used for analysis. "Invalid" results may be repeated as per protocol.

### 7.2.1. Primary Analysis

The secondary efficacy endpoints will be summarized and analyzed using the Completer Set and methods described for the primary endpoint.

---

As the endpoint is only captured once during follow-up, including the constant-valued visit identifier (AVISITN) as a class covariate will not affect the model while permitting use of the LSMEANS statement to calculate the mean change in SBP.

Daytime and nighttime windows "are best defined using sleeping times reported by individual users' diary cards". Accordingly, day/night windows subdividing the 24-hour ABPM data will be defined using on sleep/wake times captured from participant sleep diary entries on the nights where the ABPM is being used. Sleep diary times may be converted to 12- or 24-hour format as necessary to merge with ABPM entries and perform the summaries. If valid sleep diary entries covering the ABPM night are not available but other diary entries for the visit are available, the weekly mean sleep/wake time (see Section 8.1.3) may be used to create the daytime/nighttime windows (Section 5.2.4).

A supporting analysis of the daytime/nighttime SBP endpoints will be performed using fixed time windows of 09:00h to 21:00h (daytime) and 01:00h to 06:00h (nighttime) for all participants. However, if the percentage of participants with non-missing sleep diary data is below 85% (N<37 at the interim analysis; N<49 to N<66 at the final analysis), then the fixed window analysis will be considered the primary analysis (including use for statistical testing hierarchy) and the diary-based analysis will be considered supportive.

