#### **8.3.2. Vital Signs**

##### **8.3.2.1. Blood Pressure and Other Vitals**

- BP and pulse measurements should be obtained at the investigational site using the sponsor-provided device (site-based participants) or at the participant's home location with study personnel using the sponsor-provided device (decentralized participants). The same device should be used for each measurement to ensure consistency for a given participant.
- BP and pulse measurements should be preceded by at least 5 minutes of quiet rest (ie, no talking) and obtained while the participant is seated in a quiet setting without distractions (eg, television, cell phones).
- BP and pulse measurements will be obtained using a sponsor-provided OBPM device. Once initiated, this device will start a 5-minute countdown (ie, a rest period), followed by 3 consecutive BP and pulse rate measurements with 1-minute intervals between each measurement. The device will then automatically calculate and record an average for the 3 BP and 3 pulse rate readings (calculated and recorded separately for SBP and DBP).

- At the Screening Visit, BP and pulse measurements should be obtained before blood collection for laboratory tests. BP and pulse may be repeated up to 2 additional times if the investigator considers that the average recorded by the device was unduly influenced by transitory factors (eg, excessive movement or loud noises during measurement). All screening measurements should be reviewed and filed in the source documents. The investigator will select only 1 recording average for purposes of study eligibility.

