## 9.2. Analysis Sets

For the purposes of analysis, the following analysis sets are defined:

Participant Analysis Set	Description
Enrolled Set	The Enrolled Analysis Set will include all participants who provide informed consent for this study.  This analysis set will be used to summarize participant disposition, major protocol deviations (as classified in Clinical Trial Management Software), and inclusion/exclusion from the Safety Set, including reasons for exclusion from it.
Safety Set	All participants who take/receive at least 1 dose of study intervention (XYWAV).  This analysis set will be used for reporting analyses of safety endpoints and sensitivity analyses of efficacy endpoints.
Completer Set	All participants who complete the EOT Visit after 6 weeks of study intervention with a 24-hour BP recording at this visit that meets the minimal data standards.  This analysis set will be used for primary analyses of effectiveness variables.
Effectiveness Set	All participants who complete at least 1 post-baseline study effectiveness assessment (including early discontinuation).  This analysis set will be used for reporting sensitivity analyses of effectiveness endpoints.

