#### 4. ANALYSIS SETS

For purposes of analysis, the following populations are defined:

Analysis Set	Description
Enrolled Set	
The Enrolled Analysis Set will include all participants who provide informed consent for this study.
 
This analysis set will be used to summarize participant disposition, protocol deviations (as classified in Clinical Trial Management Software), and inclusion/exclusion from the Safety Set, including reasons for exclusion from it.

Safety Set	
All participants who take/receive at least 1 dose of study intervention (XYWAV).
 
This analysis set will be used for reporting analyses of safety endpoints.

Completer Set	
All participants who complete the EOT Visit after 6 weeks of study intervention with a 24-hour BP recording at this visit that meets the minimal data standards.
 
This analysis set will be used for primary analyses of effectiveness endpoints.

Effectiveness Set	
All participants who complete at least one post-baseline study effectiveness assessment (including early discontinuation).
 
This analysis set will be used for reporting sensitivity analyses of effectiveness endpoints.

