### 5.3. Hypothesis Testing

The primary statistical hypothesis for this study is that there will be a clinically relevant decrease in 24-hour average SBP, compared to baseline, after switching from high-sodium oxybate to XYWAV for 6 weeks. The null and alternative hypotheses for the primary endpoint are:

$$H_0: \Delta_{SBP} = 0; H_1: \Delta_{SBP} < 0$$

Similarly defined hypotheses will be tested for the secondary endpoints of change in daytime and nighttime average SBP (both assessed using 24-hour ambulatory BP monitors) and change in seated resting SBP (assessed using the measurements performed by the site personnel).

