## 5.4. Level of Significance & Multiplicity Adjustment

To control family-wise error rate inflation due to multiple endpoints and the interim analysis (Section 3.5), a fixed hierarchical testing sequence will be employed. Testing begins with the first endpoint at the specified alpha level and continues through the sequence until an endpoint is not statistically significant. Remaining analyses will be considered exploratory and associated p-values will be considered nominal.

The Type I error rate for study endpoints will be set at a one-sided level of 0.025. To account for the possibility of ending the study at the interim analysis, statistical significance for the primary endpoint (#1) will be assessed using O'Brien-Fleming one-sided alpha levels of 0.00998 for the interim analysis and 0.02194 for the final analysis. Statistical significance for each of the secondary endpoints (#2 to #4) will be assessed using the Pocock one-sided alpha level of 0.0168 at either the interim or final analysis.

Statistical hypotheses to be tested (in sequential order):

1. Change in the 24-hour average SBP (mm Hg) following 6 weeks of XYWAV treatment after switching from high-sodium oxybate in participants with narcolepsy
2. Change in the daytime average SBP (mm Hg) following 6 weeks of XYWAV treatment after switching from high-sodium oxybate in participants with narcolepsy
3. Change in the seated resting average SBP (mm Hg) following 6 weeks of XYWAV treatment after switching from high-sodium oxybate in participants with narcolepsy
4. Change in the nighttime average SBP (mm Hg) following 6 weeks of XYWAV treatment after switching from high-sodium oxybate in participants with narcolepsy

Analyses not part of this hierarchy will be considered exploratory, and no multiplicity adjustment will be performed. P-values reported in standard table outputs will be considered nominal.

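### The confirmatory test of seated SBP (hypothesis 3) excludes week-6 completers who have a valid seated reading but no valid end-of-treatment ambulatory recording

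*SAP*

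**What the plan says.** **Analysis set.** SAP 7.2.1 gives one rule for all three secondary endpoints: "The secondary efficacy endpoints will be summarized and analyzed using the Completer Set". The methods are those of the primary analysis. SAP 4 limits the Completer Set to those who reach the EOT Visit at 6 weeks, and it adds this condition: "with a 24-hour BP recording at this visit that meets the minimal data standards". Protocol 9.2 defines the set in the same way and adds: "This analysis set will be used for primary analyses of effectiveness variables". Neither document makes an exception for seated SBP.

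**The endpoint.** Seated SBP is third in the confirmatory sequence (SAP 5.4): "Change in the seated resting average SBP (mm Hg) following 6 weeks of XYWAV treatment after switching from high-sodium oxybate in participants with narcolepsy". Protocol 8.3.2.1 describes its measurement: "BP and pulse measurements will be obtained using a sponsor-provided OBPM device". SAP 5.3 separates it from the ambulatory endpoints as "change in seated resting SBP (assessed using the measurements performed by the site personnel". Both schedules of assessments place it at Visit 7.

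**Where ambulatory validity is required.** SAP 5.2.4 applies the adequacy criteria to ABPM-based endpoints. SAP 7.2 states the validity rule for the daytime and nighttime endpoints only.

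**Safeguards.** A valid screening recording is inclusion criterion 10. A failed recording may be repeated up to twice (Protocol 8.2.1), and participants stay on XYWAV until the EOT recording passes (Protocol 4.1). SAP 7.2.2 repeats the secondary analyses on the Effectiveness Set, which is anyone with at least one post-baseline effectiveness assessment.

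**The concern.** Seated SBP does not use the ambulatory monitor, so the only thing tying hypothesis 3 to the quality of that recording is the choice of analysis set. The visible text of the seated-SBP estimand (Protocol 3) carries no ambulatory condition, and Protocol 9.3.1.2 does not list a failed recording as an intercurrent event. The exclusion therefore removes observed on-treatment week-6 data from the main analysis of an endpoint to which the failed recording is irrelevant, and the documents give no reason for it.

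At stake is some power for hypothesis 3 and, because formal testing stops at the first non-significant result, some chance of reaching hypothesis 4 (nighttime SBP). The participants concerned completed treatment; they are not early discontinuers.

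**Working it through.** **Inputs.** Difference 3.5 mm Hg, SD 8.0, one-sided 0.025, 57 completers (SAP 3.3). One-sided 0.0168 for secondary endpoints (SAP 5.4). 67 starters for 57 completers, and up to about 91 for 77 (Protocol 9.5). The documents give no ambulatory failure rate and no effect or SD for seated SBP. The 24-hour values are borrowed, and the number of participants recovered, k, is an assumption.

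**Formula.** For a one-sample t-test on the change, power = 1 − F(t; n − 1, λ). Here F is the noncentral t distribution function, t is the upper-α critical value on n − 1 degrees of freedom, and λ = (3.5/8)·√n. Any gain from the ANCOVA baseline adjustment is ignored, as the plan's own table appears to do.

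**Step 1: the plan's figure.** At α = 0.025 and n = 57, t = 2.003 and λ = 0.4375 × √57 = 3.303, giving power 0.901. At n = 56 power is 0.896, so 57 is the smallest n that reaches 90%. All 18 cells of the power table reproduce the same way, so the plan's sample-size table is sound.

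**Step 2: hypothesis 3 at its own alpha.** At α = 0.0168 and n = 57, t = 2.178 and λ = 3.303, giving power 0.867. The drop from 90.1% to 86.7% comes from the smaller alpha, not from the analysis set.

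**Step 3: adding back k participants with a valid seated pair but no valid EOT ambulatory recording.**

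| k | n | k as share of week-6 attendees, k/(57 + k) | Power at 0.0168 |
|---|---|---|---|
| 0 | 57 | 0% | 86.7% |
| 1 | 58 | 1.7% | 87.3% |
| 3 | 60 | 5.0% | 88.5% |
| 6 | 63 | 9.5% | 90.0% |
| 10 | 67 | 14.9% | 91.8% |

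The last row is a ceiling: with 67 starters, k = 10 would need all ten non-completers to be ambulatory failures and none to be dropouts. At 77 completers power is already 95.1%, and k = 3 gives 95.8%.

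**Step 4: stopping at the interim.** The secondary endpoints are then tested at about n = 43. Power there is 74.7%, and 76.9% at n = 45 (k = 2). These figures do not condition on the primary endpoint having succeeded.

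**Step 5: possible shift in the estimate.** If the excluded participants' mean change differed from the rest by D, including them would move the estimate by k·D/(57 + k). For k = 3, D = 2 gives 3 × 2/60 = 0.10 mm Hg and D = 5 gives 3 × 5/60 = 0.25 mm Hg. Nothing in the documents indicates what D is, or that it differs from zero.

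**The case against.** **The readings are not thrown away.** A reader might infer that these seated values are lost to the study. They are not: SAP 7.2.2 brings them into the Effectiveness Set analysis. This stands. What remains is narrower: that analysis does not decide the hierarchy, is aimed at early discontinuation, and mixes these participants with early-discontinuation readings. No planned analysis isolates them.

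**Few participants should be affected.** Everyone treated has already passed a screening recording, arm circumference is measured for the cuff (Protocol 8.3.1), and three EOT attempts are possible. If attempts failed independently (an assumption; failures may cluster within a person), a final failure rate of 5% or 10% would need per-attempt rates of 0.05^(1/3) = 37% or 0.10^(1/3) = 46%. A 20% per-attempt rate leaves 0.2³ = 0.8%, or about 0.5 of a participant in 57. This stands, and it is why k = 0 and k = 1 belong in the table.

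**There is no shortfall against plan.** The target counts participants with complete data, so failed recordings do not take hypothesis 3 below 57. This also stands: the point is a gain forgone.

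**Selection.** A reader might also infer that the retained group is biased, because cuff failure could relate to arm size, disturbed sleep or high BP. The documents offer no evidence for this, and the entry recording filters out many persistent causes.

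**One common set has merit.** It keeps seated and ambulatory changes comparable in the same people, with one N, and it is prespecified consistently in both documents. That is a fair reason to report the Completer Set result, but as support; it does not require leaving valid seated data out of the confirmatory test.

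**Conclusion.** The point holds as a low-priority improvement. The text excludes from the confirmatory seated-SBP test any week-6 completer with a valid seated average and no valid EOT ambulatory recording, and nothing in the seated endpoint itself calls for that.

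The effect is probably small and may be nil: no change in power if nobody is affected, 0.6 percentage points for one participant, 1.8 for three and 3.3 for six, starting from 86.7% at n = 57. These figures rest on a borrowed effect and SD and on assumed counts. The knock-on to hypothesis 4 has not been quantified. The documents do not support the stronger conclusions that data are lost altogether, that the seated estimate is biased, or that the plan contradicts itself or misses its stated power because of this choice.

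**What to change.** In SAP 4, SAP 7.2.1 and Protocol 9.2, before the data are examined, specify that hypothesis 3 is analysed in all participants who complete the EOT Visit after 6 weeks of study intervention and have a baseline and an EOT seated average, whatever the validity of the ambulatory recording. Use the same set if the secondary endpoints are tested at the interim.

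Keep the Completer Set for the 24-hour, daytime and nighttime endpoints. Report the Completer Set result for seated SBP as supportive, and report how many participants the Completer Set excludes for ambulatory failure alone.

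Alpha levels, test order, model and data collection do not change. The cost is a slightly different N for hypothesis 3 from that of the ambulatory hypotheses, plus a small update to both documents, made through a SAP revision and a protocol amendment.

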#### **7.2.2. Sensitivity Analyses**

To assess the effect of early treatment discontinuation on the endpoint, analyses will be repeated using the Effectiveness Set.

#### **7.2.3. Subgroup Analyses**

To assess endpoint differences according to potential effect-modifying covariates, additional analyses for subgroups specified in Section 5.5 will be performed using the Completer Set and methods described for the primary endpoint.

### **7.3. Exploratory Endpoints and Analyses**

[REDACTED]

[REDACTED]

[REDACTED]

[REDACTED]

[REDACTED]

#### **7.3.1. Diastolic blood pressures (DBP)**

Analyses will follow the methods described for the primary and secondary endpoints.

---

O'Brien E, et al. European Society of Hypertension Position Paper on Ambulatory Blood Pressure Monitoring. J Hypertens 2013; 31:1731-1768.

Kario K, et al. Guidance on ambulatory blood pressure monitoring: A statement from the HOPE Asia Network. J Clin Hypertens (Greenwich) 2021 Mar; 23(3):411-421.

### 7.3.2. Nocturnal SBP dipping

Nocturnal SBP dipping magnitude is defined using the 24-hour ABPM data as the difference between average daytime SBP and average nighttime SBP expressed as a percentage of the daytime value.

$$\text{Nocturnal Dipping Magnitude (\%)} = \frac{\text{Daytime mean SBP} - \text{Nighttime mean SBP}}{\text{Daytime mean SBP}} \times 100$$

Generally accepted normal values of nocturnal dipping are between 10% and 20%. Nocturnal dipping magnitude will be classified as absent (<10%), normal ( $\geq 10\%$  to  $\leq 20\%$ ) or extreme ( $> 20\%$ ).

Nocturnal dipping magnitudes at each visit, including change from baseline, will be summarized as continuous variables. Nocturnal dipping magnitude classifications at each visit will also be summarized as categorical variables. Crosstabulations and the McNemar-Bowker test will be performed to describe change in nocturnal dipping classification between time points.

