recommended daily dose of XYREM (9 g/day) results in an intake of 1640 mg sodium/day, akin to 109% of the ideal recommended dietary allowance of sodium per day (CDC, 2010). XYREM product labeling includes warnings and precautions regarding this high sodium content, advising monitoring of patients with heart failure, hypertension, or impaired renal function (XYREM USPI). This may limit certain patients with these existing conditions from receiving oxybate therapy, as an increase in sodium intake enhances risk for cardiovascular morbidity and mortality, particularly in these at-risk individuals (Cook, 2007).

Many patients with narcolepsy have associated cardiovascular risk factors and comorbidities (Ohayon, 2014; Jennum, 2021), and an analysis of US claims data revealed that multiple conditions were more common in patients with narcolepsy, including acute myocardial infarction (OR 1.6), coronary atherosclerosis (OR 2.2), and congestive heart failure (OR 2.6) (Black, 2017). Narcolepsy is also associated with a blunted nocturnal sleep-related decrease in BP (nondipping phenomenon) (Dauvilliers, 2012). In the general population, this has been shown to confer increased cardiovascular risk independent of a diagnosis of hypertension (Ohkubo, 2002).

Existing evidence suggests that reducing daily sodium intake by 1000 to 1500 mg/day can substantially reduce cardiovascular risk (Bibbins-Domingo, 2010; Coxson, 2013; NASEM, 2019b). In addition, chronic use of medications with relatively high sodium content has been shown to significantly impact overall cardiovascular health. For instance, studies of participants who regularly use sodium-containing paracetamol formulations have demonstrated that switching to sodium-free paracetamol formulations (thus reducing daily sodium intake by approximately 1500 to 1600 mg/day) was associated with significant reductions in SBP and DBP (Ubeda, 2009; Benitez-Camps, 2018). Therefore, reducing daily sodium intake by approximately 1000 to 1500 mg/day, either through changes in diet or changes in medications, has been shown to result in clinically meaningful improvements in cardiovascular health.

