##### 5.1. General Methods

All study data will be summarized using descriptive statistics. Categorical variables (e.g., race, ethnicity) will be reported as frequency and percent. Continuous variables will be reported as number of participants, mean, SD, median, minimum, and maximum (eg, age, weight). All summaries, statistical analyses, and individual participant data listings will be performed with SAS version 9.4 or later (SAS Institute, Inc.; Cary, NC). Tables, Listings, and Figures (TLFs) specifications are in another document which is incorporated by reference.

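### SAP 7.3.2 gives the change in nocturnal SBP dipping no confidence interval or test on its own percentage scale; the one test named in the readable text uses three cut classes and has low power for shifts of about 2 points

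*SAP*

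**What the plan says.** SAP 7.3.2 defines dipping magnitude as "the difference between average daytime SBP and average nighttime SBP expressed as a percentage of the daytime value". The measure is then handled in two ways.

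- On its own scale: "Nocturnal dipping magnitudes at each visit, including change from baseline, will be summarized as continuous variables". SAP 5.1 says what such a summary contains: "Continuous variables will be reported as number of participants, mean, SD, median, minimum, and maximum". That list has no confidence interval and no p-value.
- In classes: "Nocturnal dipping magnitude will be classified as absent (<10%), normal" (10% to 20% inclusive) and extreme (above 20%). For these, "Crosstabulations and the McNemar-Bowker test will be performed to describe change in nocturnal dipping classification between time points".

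SAP 7.3.1, on the neighbouring exploratory DBP endpoints, says "Analyses will follow the methods described for the primary and secondary endpoints". Under SAP 7.1.1 that means a baseline-adjusted least-squares mean change with SE, 95% confidence interval and p-value.

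Dipping is outside the testing hierarchy. SAP 5.4 says "Analyses not part of this hierarchy will be considered exploratory, and no multiplicity adjustment will be performed".

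The introduction to SAP 7.3, the exploratory endpoint list in SAP 2.2.3 and Protocol 9.3.4 are redacted. Statements here about what is absent concern the readable text only.

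**The concern.** McNemar-Bowker tests whether the 3 x 3 table of baseline class against EOT class is symmetric. It sees only participants who cross 10% or 20%, and it makes no use of the order of the classes. Someone who moves from 2% to 9%, or from 11% to 19%, counts as unchanged. Someone who moves from 9.9% to 10.1% counts as changed. Most of the information in a paired continuous measurement is lost before the test is applied.

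What is at stake is how an exploratory result will be read. Protocol 2.2 includes blunted night-time dipping in narcolepsy in its account of cardiovascular risk, so readers will look for this result. If the only p-value beside it comes from a low-power test, a non-significant value may be taken as evidence that the switch does not affect dipping. No printed interval would show which shifts remain compatible with the data.

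**Working it through.** **1. The plan's own sample size.** The documents give no power for dipping; their only calculation is for the primary endpoint. With a difference of 3.5 mm Hg, SD 8.0 and one-sided 0.025, the normal approximation is n = (1.95996 + 1.28155)² × (8.0/3.5)² = 10.507 × 5.224 = 54.9. The noncentral t calculation gives 57 with power 0.901, which matches the plan. So n = 57 completers is used below. SAP 7.3.2 does not name an analysis set, so this is itself an assumption.

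**2. Assumed inputs.** Baseline dipping mean 6, 9 or 12%. Between-person SD and baseline-EOT correlation (6, 0.5), (7, 0.6) or (6, 0.3). True shift 2 or 3 percentage points. Two-sided 5%. None of these values is in the documents.

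**3. Paired t-test on the percentage.** SD of change = SD × √(2(1 − ρ)); noncentrality = shift / (SD of change / √57). The critical t on 56 df is 2.003.

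| SD, ρ | SD of change | Noncentrality, 2 points | Power | Noncentrality, 3 points | Power |
|---|---|---|---|---|---|
| 6, 0.5 | 6.00 | 2.52 | 70% | 3.77 | 96% |
| 7, 0.6 | 6.26 | 2.41 | 66% | 3.62 | 95% |
| 6, 0.3 | 7.10 | 2.13 | 55% | 3.19 | 88% |

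**4. What the cut points leave.** Take mean 9, SD 6. The proportion below 10% is Φ((10 − 9)/6) = 0.566 at baseline and Φ((10 − 11)/6) = 0.434 after a 2-point rise. Everyone's expected value rises by 2 points, but the net movement out of the absent class is 57 × (0.566 − 0.434) = about 7.5 people.

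**5. McNemar-Bowker on the classes.** Simulated from bivariate normal dipping percentages cut at 10 and 20, with degrees of freedom counted over the non-empty cell pairs. Ranges run over the nine scenarios; the t-test ranges are also from simulation.

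| True shift | McNemar-Bowker | Paired t-test |
|---|---|---|
| 2 points | about 20-30% | about 55-70% |
| 3 points | about 46-66% | about 88-97% |

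With 3 df fixed, the class test is weaker still: about 12-25% and 35-61%. With no true shift it rejects in about 1-4% of runs, so it is conservative at a nominal 5%.

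**6. Wider assumptions** (mean 5-12%, SD 6-8, correlation 0.3-0.6, n = 57, 3 df).

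| True shift | McNemar-Bowker | Paired t-test |
|---|---|---|
| 2 points | 8-31% | 34-80% |
| 3 points | 21-66% | 65-99% |
| 4 points | 42-93% | 88-100% |
| 5 points | 67-99% | 97-100% |

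At the shifts where the paired t-test has 80% power (about 2.0 to 3.6 points), the class test has 13-47%, median 33%.

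**7. What an interval would show.** The 95% half-width is 2.003 × SD of change / √57. That is 2.003 × 6.00 / 7.55 = 1.6 points, up to 2.003 × 7.10 / 7.55 = 1.9 points, under the inputs in step 2.

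**The case against.** The strongest reply is that the full-scale estimate is already planned. The mean and SD of the change will be printed, and a reader with n, mean and SD can compute the interval and the paired t. This stands. What is missing is a prespecified, printed interval and test, not the estimate.

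A reader might go further and infer that a real shift in dipping would usually be missed. The documents do not support that. The mean change will be visible in the table, and power depends on inputs the documents do not give. In the assumed scenarios the class test detects a 3-point shift about half the time and a 5-point shift in most runs. A reader might also infer that McNemar-Bowker is the only test planned. With the redactions, that can be said only of the readable text.

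Three further points also stand:

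- The classes answer a separate question. A higher mean percentage can reflect movement into the normal range or into the extreme range, and a test of the mean cannot tell these apart. This is a reason to keep the crosstabulation.
- The SAP gives the class test a descriptive purpose, and p-values outside the hierarchy are nominal.
- Daytime and nighttime SBP, the two components of dipping, are secondary endpoints already analysed on the full scale with intervals.

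These points limit the importance of the matter. They do not explain why dipping, which is paired and continuous like DBP, gets no interval when DBP does.

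**Conclusion.** The point holds as a minor improvement. Under the assumptions in step 2 of the working, the class test has less than half the power of a paired t-test at a 2-point shift, and about 30 to 40 percentage points less at 3 points. A non-significant class test would be weak evidence against a shift of about 2 points. The exact figures depend on assumed means, SDs, correlations and shifts. The direction was the same in every scenario tried. No confirmatory conclusion, alpha level or sample size is affected.

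**What to change.** In SAP 7.3.2:

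- Report the mean paired change in dipping magnitude (percentage points) from baseline to EOT, with a 95% confidence interval and a nominal p-value from a paired t-test. The baseline-centred ANCOVA used for DBP would also serve.
- Keep the absent, normal and extreme classes and their crosstabulation as description, because they show whether movement is into the normal or the extreme range.
- Label McNemar-Bowker supportive.
- Name the analysis set.

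In the same edit, reconcile SAP 2.1.3, which states the dipping objective for DBP, with SAP 7.3.2, which analyses SBP.

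The cost is a few lines of SAP text and one table row. No new data are needed and the testing hierarchy is untouched. The downside is one more nominal exploratory p-value.
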